7.8 SAFETY ANALYSIS

All safety analyses will be performed on treated patients.

7.8.1 Adverse events

Unless otherwise specified, the analyses of adverse events will be descriptive in nature. All analyses of AEs will be based on the number of subjects with AEs and NOT on the number of AEs.

For analysis multiple AE occurrence data on the CRF will be collapsed into an AE provided that all of the following applies:

- All AE attributes are identical (LLT, intensity, action taken, therapy required, seriousness, reason for seriousness, relationship [investigator defined drug-relatedness], outcome, AE of special interest).
- The occurrences were time-overlapping or time-adjacent (time-adjacency of 2 occurrences is given if the second occurrence started on the same day or on the day after the end of the first occurrence).

For further details on summarisation of AE data, please refer to [\(2,3\)](#).

The analysis of adverse events will be based on the concept of treatment emergent adverse events. That means that all adverse events occurring between first drug intake in extension trial till last drug intake + 7 days will be assigned to the on-treatment period and described according to randomised treatment in parent trial. All adverse events occurring before first drug intake will be assigned to 'previous trial', 'Between-trials' or 'screening'.

All adverse events occurring after the last trial drug intake will be assigned to 'residual effect period' or 'follow-up' or 'post-study' (for listings only). For details on the treatment definition, see [Section 6.1](#).

According to ICH E3 (4), AEs classified as 'other significant' needs to be reported and will include those non-serious and non-significant adverse events with

- (i) 'action taken = drug withdrawn' or 'action taken = dose reduced', or
- (ii) marked haematological and other lab abnormalities or lead to significant concomitant therapy

An overall summary of adverse events will be presented by randomised treatment in parent trial (and Total).

The frequency of patients with AEs will be summarised by randomised treatment in parent trial (and Total), primary system organ class (SOC) and preferred term (PT). This will be presented using a >5% cut-off in the CTR and repeated without the cut-off in the CTR appendices.

Separate tables will be provided for patients with other significant AEs according to ICH E3 (4), for patients with serious AEs (SAEs), for patients with severe AEs, for patients with AEs leading to dose reduction, for patients with AEs leading to treatment interruption, for patients with AEs leading to discontinuation of trial drug, for patients with investigator defined drug-related AEs, for patients with AEs leading to death and for patients with investigator defined drug-related AEs leading to death. The frequency of patients with serious adverse events occurring with incidence in preferred term > 1% will be presented as well.

In addition a table will be provided for patients with investigator defined drug-related SAEs. This will be based on the number of patients with AE events that are both serious and investigator defined drug-related.

Data will be presented over 52 weeks, 100 weeks, 148 weeks as well as over the whole trial. The SOC's will be sorted by default alphabetically; PTs will be sorted by frequency in the Total column (within SOC).

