#### **2.1.2 Primary Endpoint(s)**

The primary endpoint is the incidence (number and % of patients) of overall adverse events over the course of this extension trial.

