#### 7.3.4 Safety analyses

Adverse events will be coded using the Medical Dictionary for Regulatory Activities (MedDRA) coding dictionary. Standard BI summary tables and listings will be produced. All adverse events with an onset between start of treatment in this extension trial and end of the residual effect period (REP), a period of 7 days after the last dose of trial medication in this extension trial, will be assigned to the treatment period for evaluation.

All treated patients will be included in the safety analysis. In general, safety analyses will be descriptive in nature and will be based on BI standards. No hypothesis testing is planned.

Statistical analysis and reporting of adverse events will concentrate on treatment-emergent adverse events in this extension trial, i. e. all adverse events occurring between start of treatment in this extension trial until 7 days after last trial drug intake will be considered 'treatment-emergent'. The residual effect period is defined as 7 days.

Adverse events that start before first drug intake in this extension trial and deteriorate under treatment will also be considered as 'treatment-emergent'. Other adverse events will be assigned to the previous trial, between-trials, screening, post-treatment, or post-trial period, as appropriate.

Frequency, severity, and causal relationship of adverse events will be tabulated by system organ class and preferred term after coding according to the current version of the Medical Dictionary for Drug Regulatory Activities (MedDRA).

Laboratory data will be analysed both quantitatively as well as qualitatively. The latter will be done via comparison of laboratory data to their reference ranges. Values outside the reference range as well as values defined as clinically relevant will be highlighted in the listings. Treatment groups will be compared descriptively with regard to distribution parameters as well as with regard to frequency and percentage of patients with abnormal values or clinically relevant abnormal values.

Vital signs, physical examinations (including weight measurement), or other safety-relevant data observed at screening, baseline, during the course of the trial and at the end-of-trial evaluation will be assessed with regard to possible changes compared to findings before start of treatment.

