3. INTRODUCTION

As per ICH E9 (1), the purpose of this document is to provide a more technical and detailed elaboration of the principal features of the analysis described in the protocol, and to include detailed procedures for executing the statistical analysis of the primary and secondary variables and other data.

This TSAP assumes familiarity with the Clinical Trial Protocol (CTP), including Protocol Amendments. In particular, the TSAP is based on the planned analysis specification as written in CTP Section 7 “Statistical Methods and Determination of Sample Size”. Therefore, TSAP readers may consult the CTP for more background information on the study, e.g., on study objectives, study design and population, treatments, definition of measurements and variables, planning of sample size, randomisation.

In this document, the parent trial refers to SENSISCIS[®] or 1199.340 trial. All analyses will be done in patients coming from both SENSISCIS and 1199.340 trials. In addition, a selected set of analyses will be repeated in patients coming from SENSISCIS only.

SAS[®] Version 9.4 (or later) will be used for all analyses.

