4. CHANGES IN THE PLANNED ANALYSIS OF THE STUDY

The following further categorical endpoints were added:

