6. GENERAL ANALYSIS DEFINITIONS

6.1 TREATMENT(S)

For treatment specifications, see Section 4 of CTP.

The different periods of interest, as per CTP flow chart, are the following:

Note: the last day of each of the periods is excluded from the period. It defines the first day of the subsequent period.

- Previous trial:
 - If date of informed consent in 1199.225 and first trial drug intake in 1199.225 occur after or on last trial drug intake in SENCIS plus 28 days plus one day or date of trial completion in parent trial (SENCIS or 1199.340) plus one day, then previous trial period is defined as:

from informed consent in parent trial to the last trial drug intake in SENCIS plus 28 days plus one day or to the date of trial completion in parent trial (SENCIS or 1199.340) plus one day, whichever occurs later
 - If date of informed consent in 1199.225 or first trial drug intake in 1199.225 occur before last trial drug intake in SENCIS plus 28 days plus one day or date of trial completion in parent trial (SENCIS or 1199.340), then previous trial period is defined as:

from informed consent in parent trial to date of informed consent in 1199.225
- Between-trials (optional^[a]): from end of previous trial period (see above) to date of informed consent in 1199.225
- Screening (optional^[a]): from date of informed consent in 1199.225 to first trial drug intake in 1199.225
- Treatment period: from first trial drug intake in 1199.225 (or re-start of treatment if interruption) to last trial drug intake (or date of interruption if interruption) plus one day
- Off-treatment (optional^[a]): from date of start of interruption to re-start of treatment
- Residual effect period: from the last trial drug intake plus one day to last trial drug intake plus 7 days plus one day
- Follow-up (optional^[a]): from last trial drug intake plus 7 days plus one day (after residual effect period) to date of last contact as collected in the end of study CRF page plus one day. This period is only created if last trial drug intake took place more than 7 days before the last contact as collected in the end of study CRF page.

- Post-study: from the last trial drug intake plus 7 days plus one day to database lock or from the date of last contact as collected in the end of study CRF page (after follow-up period) plus one day to database lock, whichever occurs later

[a] This period is optional insofar as it does not necessarily exist for all patients.

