7.8.1.5 Time at risk analyses

Time at risk analyses of AEs over 1199.225 trial will be presented. Time at risk and incidence rates per 100 patient years will be calculated based on the first onset of an AE in the extension trial.

For a specific AE, the total AE time at risk [years] is defined as the sum of time at risk [days] across all contributing patients / 365.25, with for each patient the time at risk [days] defined as follows:

- Date of first onset of the AE – date of first study medication administration in extension trial +1 day for patients with the specific AE
- End of time at risk – date of first study medication administration in extension trial + 1 day for patients without the specific AE. The end of time at risk is the min (date of last trial drug intake + 7 days, database lock date).

The AE incidence rate [1/100 Patient years (pt-yrs)] = $100 * \text{number of patients with specific AE} / \text{total specific AE time at risk [years]}$

A summary by randomised treatment in parent trial (and Total), primary system organ class (SOC) and preferred term (PT) will be presented.

Separate tables will be provided for patients with other significant AEs according to ICH E3 (4), for patients with serious AEs (SAEs), for patients with severe AEs, for patients with AEs leading to permanent dose reduction, for patients with AEs leading to permanent dose discontinuation, for patients with investigator defined drug-related AEs and for patients with AEs leading to death, for investigator defined drug-related SAEs, for investigator defined drug-related AEs leading to death and pre-specified AESI. The summary of patients with SAEs will also be presented restricted to incidence in preferred term > 1%.

Time at risk analyses of AEs, investigator defined drug-related AEs and SAEs within groupings by system will be also summarised by randomised treatment in parent trial (and Total), safety topic and preferred term.

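### SAP 7.8.1 puts every adverse event that begins before first intake in an earlier period, which contradicts the protocol rule that such events count as treatment-emergent if they worsen on treatment

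*SAP*

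**What the plan says.** Protocol 2.1.2 sets a patient-level endpoint: "The primary endpoint is the incidence (number and % of patients) of overall adverse events over the course of this extension trial".

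Protocol 7.3.4 gives two routes into the treatment-emergent class. The first is onset from first extension intake to 7 days after the last. The second covers earlier onset: "Adverse events that start before first drug intake in this extension trial and deteriorate under treatment will also be considered as" treatment-emergent. Only events that meet neither route go to the previous-trial, between-trials, screening or post-treatment periods.

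SAP 7.8.1 keeps the first route: "all adverse events occurring between first drug intake in extension trial till last drug intake + 7 days will be assigned to the on-treatment period". It then says: "All adverse events occurring before first drug intake will be assigned to" the previous-trial, between-trials or screening period. SAP 6.1 defines the periods by date alone, with screening running from extension consent to first intake. SAP 7.8.1.5 adds incidence rates that are "calculated based on the first onset of an AE in the extension trial".

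The SAP's introduction states that "the TSAP is based on the planned analysis specification as written in CTP Section 7", the section that holds the worsening rule. The visible part of SAP Section 4 reads only "The following further categorical endpoints were added", and its list is not shown. For the AE sections, the readable entries in the SAP history table concern only the display of results over 52, 100 and 148 weeks and the whole trial.

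**The concern.** A programmer who follows the SAP literally would classify AEs by onset date and stop there. An AE that began mildly in screening and became severe or serious on nintedanib would stay in the screening period, although the protocol counts it as treatment-emergent.

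The events concerned are informative ones. Protocol 1.4 notes that these patients may already have gastrointestinal symptoms, and former placebo patients meet nintedanib for the first time here. Diarrhoea that starts in screening and becomes severe after the first dose could be missing from the SAP 7.8.1 tables of severe events, serious events, and events leading to dose reduction or discontinuation. It could also be missing from the worst-intensity summary in SAP 7.8.1.4. Any loss runs one way, towards fewer events on drug.

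**Working it through.** The documents state no AE rate, worsening rate or count of screening AEs, so there is no plan figure to reproduce. The check follows each kind of pre-intake event through both rules.

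**Inputs on recording.** AEs ongoing from a parent trial are entered as baseline conditions (Protocol Flowchart footnote 4; 6.2.1). Worsening of a baseline or pre-existing condition is entered as an AE (Protocol 5.2.1, 5.2.2, 5.2.11.2). AEs are collected from extension consent (Protocol 5.2.11.2). The SAP merges occurrences only if every listed attribute, including intensity and seriousness, is the same (SAP 7.8.1).

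| Event | Protocol 7.3.4 | SAP 7.8.1 |
|---|---|---|
| Carried over from parent trial, worsens on drug, entered as a new AE dated at worsening | counted | counted |
| Starts between consent and first intake, worsens, worsening entered as a separate occurrence | counted | counted: not merged, keeps its own on-treatment onset |
| Starts between consent and first intake, worsens, kept as one record with its original onset | counted | **not counted**: screening |
| Starts before first intake, does not worsen | not counted | not counted |

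The rules part mainly in the third row. That row is empty, or nearly so, where Visits 1 and 2 share a day. This is always planned for patients from 1199-0340, and is allowed for SENSCIS patients whose last laboratory test was within 6 weeks of Visit 2.

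**Primary endpoint.** A patient in the third row leaves the any-AE count only if they have no other on-treatment AE. Let k be the number of such patients and p the share of patients with another on-treatment AE. Under independence the loss is k × (1 − p).

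All rates below are assumptions:
- Take 100 to 200 patients with a separate screening period, 10% to 20% of them with an AE in it, and 10% to 25% of those worsening on drug with none re-entered. Then k runs from 100 × 0.10 × 0.10 = 1 to 200 × 0.20 × 0.25 = 10.
- With p from 98% down to 80%, the loss runs from 1 × 0.02 = 0.02 to 10 × 0.20 = 2 patients. Of the 400 + 14 = 414 anticipated patients, 2 is 0.48 percentage points. If all 10 had no other AE, it would be 10/414 = 2.4 points.
- A much wider range puts 2% to 20% of all 414 patients in the third row. Under independence this gives 414 × 0.02 × 0.02 = 0.17 patients (0.04 points) to 414 × 0.20 × 0.20 = 16.6 patients (4.0 points). The top end needs 414 × 0.20 = 83 such patients, which is hard to reconcile with so restricted a group.

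**Other tables.** For a given preferred term, severity or seriousness class, an AE under another term does not make up for the missing one. In the rate tables the patient is missing from the numerator and, as a patient without the event, contributes time up to last intake plus 7 days to the denominator. Both lower the rate.

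**Dating.** SAP 7.8.1.5 sets time at risk as onset date minus first-dose date plus 1. If the protocol rule were restored with the original onset kept, an AE that began 10 days before first dose would give −10 + 1 = −9 days. A restored rule therefore needs a dating convention.

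**The case against.** The strongest reply is that the recording rules already do what the protocol sentence asks. AEs carried over from the parent trials, a main source of pre-intake events, are baseline conditions whose worsening becomes a new AE. Even an AE that starts in screening might be handled that way: the Flowchart records baseline conditions at both Visit 1 and Visit 2, and worsening of pre-existing conditions in general is to be entered as an AE. A separately entered occurrence of higher intensity is not merged. This stands, and it narrows the point. It does not close it, because no visible text requires a site to split a screening AE when it worsens.

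It can also be said that the SAP rests on protocol Section 7 and leaves AE detail to sponsor standards that are not available here, while the list in SAP Section 4 is not shown. It therefore cannot be established that the rule was dropped on purpose, or that it is absent from programming. But if a standard applies the rule, the SAP's unqualified sentence conflicts with that standard as well as with the protocol.

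Two stronger readings are tempting. A reader might infer that worsened events as a class leave the primary endpoint. The recording rules, the merging rule and the patient-level count do not support that. A reader might also take the 12-week limit as the length of the screening window. Those weeks run from last SENSCIS intake to Visit 2, not from consent, and time between the trials is a separate SAP period. Lastly, SAP 7.8.1.5 produces no negative time as the SAP now stands, because these events are excluded. The problem arises only once they are included.

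**Conclusion.** SAP 7.8.1 is wrong as written: it states a rule that contradicts protocol 7.3.4 on the case definition behind the primary endpoint, and no visible text declares the change. The consequence is confined mainly to AEs that start between extension consent and first intake, worsen on nintedanib and are kept under their original onset date.

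The effect on the any-AE incidence is probably very small and cannot be quantified from the documents; the ranges above rest wholly on assumed rates. Preferred-term, severe, serious and incidence-rate tables are more exposed, and their error would be an understatement. The analysis is descriptive, so no test or power is affected. The correction should be made because the conflict is explicit and the remedy is nearly free.

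**What to change.** Restore the protocol rule in SAP 7.8.1, and add the matching exception to the period assignment in 6.1. Suggested text:

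*An AE with onset before first intake in the extension trial that increases in intensity or becomes serious between first intake and last intake plus 7 days is assigned to the on-treatment period (CTP 7.3.4). All other AEs with onset before first intake are assigned to the previous-trial, between-trials or screening period.*

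The protocol does not define deterioration, so the intensity-or-seriousness criterion is a proposed way to make it operational.

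In SAP 7.8.1.5, use the date of worsening as the onset of such an event for time at risk, and say how that date is set when the record does not hold one.

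The cost is a short text change and one extra derivation in the AE dataset. A few more events may be counted as on-treatment, as the protocol intends.

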7.8.1.1 Pre-specified adverse events of special interest

Gastrointestinal perforations and hepatic injury are adverse events of special interest (AESI) pre-specified in the CTP Section 5.2.11.1. These are investigator reported on the eCRF and will be identified using this information for this analysis. The frequency of patients with pre-specified AESI will be summarised by randomised treatment in parent trial (and Total), primary SOC and preferred term (PT).

7.8.1.2 Adverse events with additional information collection

Diarrhoea and bleeding are AEs with additional AE-specific information collected on the eCRF. These are investigator reported on the eCRF and will be identified using this information for this analysis. That is if the diarrhoea information has been completed for an adverse event then the adverse event will be considered as diarrhoea for this analysis regardless of subsequent MedDRA coding of the verbatim term. Likewise, if the bleeding information has been completed for an adverse event then the adverse event will be considered as bleeding for this analysis regardless of subsequent MedDRA coding of the verbatim term.

The additional information collected will be summarised at the AE level (occurrence level) rather than at the patient level separately for diarrhoea and bleeding.

Bleeding AEs will also be summarised by system and safety topic, see Section 7.8.1.3 for further details.

For the above mentioned analyses, data will be presented over 52 weeks, 100 weeks, 148 weeks as well as over the whole trial.

7.8.1.3 Additional analysis of adverse event groupings by system

Further adverse event groupings by system and safety topic have been defined outside the trial protocol as medically relevant to the clinical development program and are specified in (8).

The frequency of patients with AEs within these groupings will be summarised by system, randomised treatment group in the parent trial (and overall), safety topic and preferred term. Separate tables will be provided for patients with investigator defined drug-related AEs, serious AEs (SAEs), drug-related serious AEs and bleeding AEs. Data will be presented over 52 weeks, 100 weeks, 148 weeks as well as over the whole trial.

7.8.1.4 Adverse events of particular note

Gastro-intestinal adverse events (diarrhoea, nausea, vomiting, dehydration, weight decrease and decreased appetite) are considered as AEs of particular note.

Specific tables will be created in order to describe adverse events of particular note in the extension trial:

- Summary of AEs including intensity, seriousness, clinical consequences (permanent dose reduction, drug discontinuation or drug interruption), drug relationship, therapy for event and outcome
- Summary of AEs including time to onset, number and duration of episodes

In the summary of adverse events of particular note including intensity, seriousness, clinical consequences, drug relationship, therapy for event and outcome: for patients with several episodes, the worst intensity, relationship, outcome and clinical consequence during on-treatment period will be displayed. For clinical consequences, the worst category is

considered to be “Drug withdrawn”, then “Dose reduced”, “Dose not changed” and finally “Dose increased”. Worst to best outcome are: “Fatal”, “Recovered/Resolved with sequelae”, “Not Recovered/Not Resolved”, “Recovered/ Resolved”, “Unknown”.

Depending on the number of patients having such AEs, a Kaplan-Meier plot of time to first adverse event of particular note may be drawn by randomised treatment in parent trial (and Total).

In addition, for pairs of selected adverse events (from diarrhoea, nausea, vomiting, decreased appetite, dehydration, weight decreased as defined in (8)), the frequency of patients with concurrent AEs will be summarised by treatment where concurrence is defined as an overlap of at least one day.

